6.1.1 Primary Efficacy Measure

The primary efficacy measure is IELT as measured by stopwatch.

The IELT is captured on the SID and provides an objective assessment of the pharmacologic effects of study treatment on PE.

The primary efficacy variable will be change from baseline in the logarithm value of individual patient's geometric mean IELT across all the evaluable ejaculatory attempts recorded in the SIDs at the end of the randomized 12 week follow-up period.

Examination Procedures, Tests, Equipment, and Techniques

Study evaluations and treatments must be performed by the same investigator/sub-investigator throughout the study whenever possible (see Table 1 and Table 2). If it is not possible for the same individual to follow the patient, then an attempt should be made to have visits overlap (examine the patient together and discuss findings) for at least one visit.

6.3.1 Medical History, Physical Examination, and Vital Signs

6.3.1.1 Medical History

A standard medical history (including all relevant conditions that the patient has had in the past or currently has) must be obtained at screening and before randomization at the treatment visit (day 1).

A sexual history must also be obtained including usage and duration of usage of all previous self-initiated or health-care-professional prescribed treatments/therapies/techniques for PE (may include, but not limited to behavioral therapies, distraction techniques, topical or oral therapies, use of condoms, etc).

All medical and surgical procedures must have an associated medical history entry.

6.3.1.2 Physical Examination

A physical examination will be performed at screening and at week 12 (exit visit) of the randomized period and at week 12 of the open-label period of Cohort 6 (study exit for open label). The investigator will examine the patient for any physical abnormality of the following systems: general appearance; head, eyes, ears, nose, and throat; heart/cardiovascular; lungs; abdomen; neurologic; extremities; back; musculoskeletal; lymphatic; skin; genitourinary; and rectal. The patient's weight will also be measured. The patient's height will only be measured at the screening visit.

6.3.1.3 Vital Signs

Vital signs will be measured at screening, treatment/day 1 (prior to injection and prior to leaving the clinic), and all follow-up clinic visits. The following vital signs will be measured:

- pulse rate (beats per minute): the patient should be resting in a seated position for a minimum of 5 minutes prior to measurement. Pulse rate is then counted over 30 seconds (× 2).
- blood pressure (mm Hg): the patient must be resting in a seated position for a minimum of 5 minutes prior to measurement. Systolic/diastolic blood pressure will be measured with a sphygmomanometer.
- temperature (°C/°F): temperature assessment method must be performed consistently throughout the study.

6.3.2 Blood Specimen Procedures

Blood samples will be obtained for the analyses of hematology and non-fasting serum chemistry.

A central laboratory will be used to analyze all blood specimens, including any repeat laboratory tests. Instructions for the collection, processing, shipment, and storage of blood samples are provided in the central laboratory manual.

All hematology and serum chemistry laboratory test results will be:

forwarded from the central laboratory to the study site and to Allergan or its designee

- reviewed by the investigator for the clinical significance of any abnormalities
- evaluated and managed, if the laboratory result is abnormal, and conducted according to local site practice
- recorded on an adverse event electronic case report form (eCRF) page, for any clinically significant abnormalities

The laboratory results from the screening period must be reviewed prior to randomization (including the most recent results if any investigations were repeated), and randomization/treatment administration must only be performed if the investigator deems the results to be acceptable.

6.3.2.1 Hematology

Hematology blood samples are to be collected at screening, week 4, and week 12 of both the randomized period and the open-label period.

Hematology measures are as follows: hematocrit, hemoglobin, mean corpuscular hemoglobin, mean corpuscular hemoglobin concentration, mean corpuscular volume (MCV), platelets, red blood cell (RBC) count, RBC morphology, total white blood cell (WBC) count and differential (eg, neutrophils, bands, lymphocytes, monocytes, basophils, and eosinophils).

6.3.2.2 Serum Chemistry

Nonfasting serum chemistry blood samples are to be collected at screening, and weeks 4 and 12 of both the randomized period and the open-label period.

Serum chemistry measures are as follows: albumin, alkaline phosphatase, alanine transaminase, aspartate transaminase, bicarbonate, calcium, chloride, creatinine, creatine kinase, direct bilirubin, non-fasting glucose, indirect bilirubin, magnesium, phosphorous, potassium, sodium, total bilirubin, total cholesterol, total protein, urea nitrogen, and uric acid.

6.3.3 Urine Specimen Procedures

Urine samples will be obtained for central laboratory urine analysis and for urine culture and sensitivity.

A central laboratory will be used to analyze all urine specimens, including any repeat laboratory tests. Instructions for the collection, processing, shipment, and storage of urine samples are provided in the central laboratory manual.

All urine laboratory test results will be:

- forwarded from the central laboratory to the study site and to Allergan or its designee
- reviewed by the investigator for the clinical significance of any abnormalities
- evaluated and managed, if the laboratory result is abnormal, and conducted according to local site practice
- recorded on an adverse event eCRF page, for any clinically significant abnormalities

The laboratory results from the screening period must be reviewed prior to randomization (including the most recent results if any investigations were repeated), and randomization/treatment administration must only be performed if the investigator deems the results to be acceptable.

6.3.3.1 Central Laboratory Urine Analysis

Urine samples are to be collected at screening, and weeks 4 and 12 of both the randomized period and the open-label period.

The urine will be analyzed for clarity, color, bilirubin, blood, glucose, ketones, leukocyte esterase, nitrite, pH, protein, specific gravity, urobilinogen, microscopic sediment (WBCs, RBCs, casts, bacteria, crystals, and epithelial cells).

6.3.3.2 Urine Culture and Sensitivity

The urine culture and sensitivity sample will be analyzed as a reflex (automatic) test by the central laboratory when the central laboratory urine analysis results are suggestive of a urinary tract infection (eg, positive leukocyte esterase, nitrites, blood, or microscopic sediments such as WBCs, RBCs, and/or bacteria).

6.3.4 Intravaginal Ejaculatory Latency Time

Patients will document sexual activities in the SID during screening and for 12 weeks following treatment to provide baseline and posttreatment IELT data.

Either the patient or female partner may operate the stopwatch, although the preference is for the female partner to operate the stopwatch. The stopwatch operator must be consistent throughout screening and the posttreatment period.

In the SID, patients will be asked to record the date and start time of each sexual encounter, the duration of intercourse (ie, the time from vaginal penetration until ejaculation, measured with a stopwatch), and a description of when the ejaculation occurred (ie, prior to penetration, intravaginal, did not occur, or after withdrawal) for all sexual intercourse attempts.

Patients must be instructed:

- that any behavioral techniques that were performed prior to screening should also be continued consistently for the duration of the study
- that the patient and female partner must not significantly alter their normal sexual practices during the course of the study (eg, amount of foreplay, use of lubrication, or position).
- that condoms must not be used during the study
- not to withdraw the penis from the vagina during intercourse as this would make the event nonevaluable
- to record all sexual intercourse events that constitute an attempt at penile penetration of the vagina, including any ejaculation that occurs before, during, or after the act of vaginal penetration
- that if ejaculation does not occur during intercourse and a new vaginal penetration is attempted, these separate vaginal penetrations must be recorded on the SID as 2 separate events

Additional study site instructions regarding the SID are provided in Attachment 12.2.

Sexual events recorded on the SID will be reviewed by the site and/or Allergan (or designee) to determine if the events are evaluable.

6.3.4.1 Definition of Evaluable Intravaginal Ejaculatory Latency Time Events

An evaluable event is defined as:

• an event in which the patient and his female partner had vaginal intercourse, and the couple have recorded that the ejaculation occurred 'intravaginally' and duration of time from penetration to ejaculation has been recorded

OR

an event in which the patient and his female partner attempted to have vaginal
intercourse. However, the couple have recorded that ejaculation occurred "prior to
vaginal penetration". In this scenario, the duration of time will be recorded as zero for
the purpose of calculating the average IELT.

Any other scenarios will not be considered as evaluable and must not be included in the screening average IELT calculation.

6.3.4.2 Screening Intravaginal Ejaculatory Latency Time Collection

The patient will receive a stopwatch, the SID and written instructions during screening. The site will also provide training on the usage of the stopwatch and SID to the patient and female partner.

Patients who are taking medications that require a washout must be instructed not to commence IELT data collection until the day after the washout period has completed.

The couple must be instructed to record at least 4 evaluable attempts at vaginal sexual intercourse during a maximum of 28 days. Patients who do not record 4 evaluable events in a period of 28 days will not be eligible for study entry. Sites may contact the patient via telephone (at the sites discretion) to determine if the patient has achieved 4 evaluable events prior to the patient returning to the site for review of the SID and determination of eligibility. There is no minimum time period to collect the 4 evaluable events (more than 4 evaluable can be collected).

Eligibility will be determined from the 4 most recent evaluable events recorded on the SID during the screening period (see Section 4.3).

- The mean (average) IELT of these 4 most recent evaluable events must be \leq 1 minute.
- None of these 4 most recent evaluable events can have an IELT ≥ 2 minutes. If any one of the 4 most recent evaluable events is ≥ 2 minutes, the patient is ineligible for study participation.

The site should determine which events are evaluable using the definitions in Section 6.3.4.1. If there is any ambiguity regarding if an event is evaluable the site should contact Allergan for clarification. Allergan will confirm the average IELT prior to patient randomization.

Note: if > 4 events have been recorded during screening then all events must be reported on the eCRF whether or not the event is evaluable; although, only the 4 most recent evaluable events will be used to determine eligibility as described above.

6.3.4.3 Posttreatment Intravaginal Ejaculatory Latency Time Collection

Patients will be instructed to refrain from having intercourse for at least 48 hours posttreatment. Patients will be reminded of the correct collection of IELT data and completion of the SID.

The couple will be instructed to record all posttreatment sexual intercourse events in the same manner as for the screening assessment, until they exit the study.

[figure not shown]
The couple will be instructed to aim for a minimum of 4 evaluable events per month and their sexual practices must remain consistent with their practices prior to study entry and during the screening period (see Section 4.6).

Patients are to be reminded to bring the SID to all study clinic visits. The site must record all available events (evaluable and not evaluable) in the eCRF.

6.3.5 Masturbatory Events

Sentinel Patients (Cohorts 1-5) must attempt at least 2 masturbations (starting 48 hours after treatment) prior to the week 1 visit. These masturbations are to be that any safety issues related to ejaculation can be identified early and reported to the DRC prior to opening the remainder of the cohort for enrollment (see Section 3.1).

Nonsentinel Patients (Cohorts 1-6) are not required to perform masturbation nor complete the unless they complain of difficulty or an adverse event related to ejaculation (see Section 6.3.5.2).

6.3.5.2 Ejaculation Adverse Events

Adverse events related to ejaculation are whenever possible to be based on findings during masturbation. If the patient complains of an ejaculation issue during nonmasturbatory situations (eg, vaginal intercourse), the site must ask the patient to confirm the findings during masturbation (if possible) and to record the finding on the finding as an adverse event. If the patient declines to perform a masturbation and/or completion of the finding the source documentation.

If the patient was unable to ejaculate despite sufficient manual stimulation and sufficient sexual arousal (in the patient's opinion) and the patient did not feel that with continued stimulation that ejaculation could be achieved then this must be recorded as:

- an adverse event of "delayed ejaculation" if the period of manual stimulation was < 30 minutes
- an adverse event of "anejaculation" if the period of manual stimulation was ≥ 30 minutes

For other ejaculation difficulties during masturbation this must be recorded as:

[figure not shown]
- an adverse event of "retrograde ejaculation", if the patient felt that ejaculation/orgasm occurred but no semen was expelled during or immediately following ejaculation
- an adverse event of "weak ejaculation", if ejaculation/orgasm occurred but the perceived force/strength of the ejaculation was noticeably reduced
- an adverse event of "dribbling ejaculation", if ejaculation occurred but the semen only dribbled out during the ejaculation or shortly after the ejaculation
- an adverse event of "painful ejaculation", if ejaculation occurred and was associated with pain for the patient

[figure not shown]
If the patient is unable or unwilling to attempt masturbations (due to religious or other reasons) then the investigator must attempt to determine the character of the ejaculatory abnormality by taking a detailed history from the patient (eg, regarding ejaculation during vaginal intercourse). In such situations, the investigator will categorize the adverse event based on their best judgment.

6.3.6 Questionnaire Assessments

The versions of the questionnaires provided in Attachment 12.1 of this protocol are examples and in practice will be replaced with the appropriate versions for the country where the questionnaire will be administered.

Questionnaires must be administered prior to the patient undergoing any procedures at the study visit.

6.4 Other Study Supplies

The following will be provided by Allergan:

- all supplies needed for blood and urine sampling (except syringes and needles)
- needles for injection of study medication

- materials for shipment of laboratory samples to central laboratory
- stopwatches
- paper data collection materials (eg, questionnaires, SID,

The following will be provided by the investigator:

- syringes and needles (for reconstitution of study medication, blood sampling, and local anesthetic administration, if applicable)
- equipment for ultrasound guided treatment administration (eg, ultrasound machine, suitable ultrasound probe, ultrasound gel, and if applicable needle guides);
 Note: ultrasound equipment may be provided by Allergan if requested by the site
- sterile pads
- antiseptic solution/wipes for cleaning treatment injection area
- local anesthetic medication and sedation (if applicable)
- sterile saline (0.9% without preservative) as diluents
- appropriate electronic connections to access study-related systems (eg, high-speed internet, telephone)

6.5 Summary of Methods of Data Collection

An IVRS/IWRS will be used to assign patient identification numbers, patient initials, randomize patients, and manage study medication inventory.

Data for this study will be collected using eCRFs via an electronic data capture system.

Source documents will be used at the sites and may include, but are not limited to, a patient's medical record, hospital charts, clinic charts, the investigator's patient study files, still capture images and video recordings as well as the results of diagnostic tests such as laboratory tests.

A qualified central laboratory will be used for the analysis of all blood and urine samples. Laboratory data will be transferred to Allergan on a periodic basis throughout the study.

7. Statistical Procedures

The final analysis will be performed when all patients have completed or exited the study. A detailed analysis plan will be finalized prior to the study database lock.

7.1 Analysis Populations

There are 3 analysis populations: modified intent-to-treat (mITT), per protocol (PP) and safety:

- The mITT population will be used to analyze all efficacy variables; the mITT population is defined as all randomized patients that have received study medication and have postbaseline IELT data available. Analyses on the mITT population will be based on the dose actually received by the patient.
- The PP population includes patients in the mITT population who have had no significant protocol deviations and will also be used for analyzing the primary efficacy variable and summarizing baseline characteristics.
- The safety population includes all treated patients and will be used in the analysis of all safety data.

7.2 Collection and Derivation of Primary and Secondary Efficacy Assessments

7.2.1 Primary Efficacy Variable

The primary variable for assessing the efficacy of BOTOX versus placebo will be the change from baseline in logarithm value of the individual patient's geometric mean IELT for the entire 12 weeks of the randomized period of the study. Only evaluable events on the logs will be used to calculate the geometric mean IELT. Nonevaluable events will not form part of the calculation. Data handling conventions including missing data imputation will be discussed in detail in the statistical analysis plan.

7.2.2 Secondary Efficacy Variables

- geometric mean IELT up to week 2, 4, 6, 8, and 10, respectively
- average IELT up to week 2, 4, 6, 8, 10, and 12, respectively

7.3 Hypothesis and Methods of Analysis

7.3.1 Primary Efficacy Analyses

The primary timepoint for analysis is week 12.

The primary null hypothesis: At the primary efficacy timepoint the difference in mean change from baseline in logarithm value of the geometric mean IELT between placebo and BOTOX is at zero; and there is no dose response shown in the change from baseline in logarithm value of the geometric mean IELT.

The primary alternative hypothesis: At the primary efficacy timepoint the difference in mean change from baseline in logarithm value of the geometric mean IELT between placebo and BOTOX is not equal to zero; or there is a dose-response in the change from baseline in logarithm value of the geometric mean IELT.

The primary efficacy variable (change from baseline in the logarithm value of individual patient's geometric mean IELT) in relation to dose levels will be analyzed using an analysis of covariance (ANCOVA) model with treatment as the fixed effect and baseline logarithm value in geometric mean IELT as the covariate to assess the relationship of response across the BOTOX dose levels. Geometric means of the IELT up to week 12 will be log-transformed prior to analysis.

No multiplicity adjustment will be taken.

Analysis of the primary efficacy variable using a PP population will also be performed.

The log-transformed primary efficacy variable will also be analyzed with a linear regression model to assess the dose-response of the active treatments.

Details will be specified in the statistical analysis plan.

7.3.2 Secondary Efficacy Analyses

[figure not shown]
The following key secondary efficacy variables will be analyzed using ANCOVA, with the treatment as factor and with baseline value as a covariate:

[figure not shown]
- log-transformed geometric mean IELT up to week 2, 4, 6, 8, and 10, respectively
- average IELT up to week 2, 4, 6, 8, 10, and 12, respectively

• interval-based geometric mean IELT and average IELT for week 4, 8, and 12 (ie, events between baseline and week 4, between week 4 and week 8, and between week 8 and week 12)

Responder analyses using the fold-change threshold of 3, 4, 5, 6, 7, and 8 in the geometric mean IELT will also be conducted.

In addition, geometric mean IELT at visits will be analyzed using a likelihood-based Z-score, as well as a bootstrap test for pair-wise comparisons between each active treatment group and the placebo (Zhou et al, 1997). Nonparametric analysis including, but not limited to the Wilcoxon rank-sum test will also be performed on the geometric mean IELT. Details will be provided in the statistical analysis plan.

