- Change from baseline is calculated as follow-up minus baseline, and treatment difference will be calculated as BOTOX[®] minus placebo.
- The type III sums of squares will be used for all analysis of covariance (ANCOVA) and analysis of variance (ANOVA) models.
- Unless otherwise specified, comparisons on categorical data will be performed using Pearson's Chi-square test. When 25% or more of the cells have expected counts of less 5, Fisher's exact test will be used.
- Except for AE and medication onset/stop dates, missing data will not be imputed.

3. Disposition and Exit Status

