3.2 Disposition and Exit Status

For each analysis population (safety, mITT and PP), patient disposition (enrolled, completed, discontinued, and reasons for discontinuation) will be presented by treatment group. A cumulative frequency table showing patient disposition (continuing, completed, discontinued and reasons for discontinuation) will be provided for the mITT population by visit. A by-patient data listing presenting exclusions from the PP analyses and the primary reason(s) for exclusion will be provided.

The exit status of the patients is classified as completed or discontinued. The reason for discontinuation include adverse event, lack of efficacy, lost to follow-up, personal reasons, protocol violation and other. A listing of discontinued patients with exit reasons will be provided.

Enrollment by site will be tabulated with the number and percent of patients screened, randomized, treated, completed and discontinued.

The summaries will be provided for both the randomized period and for the open-label period of the study, where applicable.

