5.3 Secondary Efficacy Analyses

Secondary efficacy variables include the following:

- Geometric mean IELT up to weeks 2, 4, 6, 8 and 10 of the randomized period, respectively.
- Average (arithmetic mean) IELT up to weeks 2, 4, 6, 8, 10 and 12 of the randomized period, respectively

Interval-based geometric mean IELT and average IELT for week 4, 8 and 12 (ie, events between baseline and week 4, between week 4 and week 8, and between week 8 and week 12) will also be calculated from the above two as differences between periods.

All analyses on the secondary efficacy variables will not be window-based as indicated in Section 2.2. The target day for each time point, except for week 12, will be used to determine to which interval or period a certain event belongs to. For example, all events on or before week 10 target day, day 70, will be included for analyses with IELTs up to week 10, while all events between day 29 (inclusive) and day 56 (inclusive) will be included for analyses with IELTs between week 4 and week 8. Any event data collected on or after the week 12 target date of day 84 of the randomized period, and before the day 1 (treatment day) of the open-label period, if applicable, will be included in analyses related to week 12.

Comparisons will be made for each active BOTOX[®] dose level vs. placebo without multiplicity adjustment.

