5.3.1 Secondary Efficacy Analysis

Summary statistics will be provided for each of the secondary efficacy variables. Change from baseline in log-transformed geometric mean IELTs and change from baseline in average mean IELTs will also be calculated and summarized.

Same ANCOVA model used in Section 5.2.1 will be used to the change from baseline in the log-transformed geometric mean IELT up to weeks 2, 4, 6, 8, and 10, respectively as well as change from baseline in interval-based log-transformed geometric mean IELT for weeks 4, 8

and 12, with treatment as the fixed effect, and log-transformed baseline geometric mean IELT as the covariate.

Summary statistics will be provided for average IELT as well as change from baseline in average IELT by timepoint. A similar ANCOVA model will be used on change from baseline in average IELT as well as the interval-based average IELTs: the model will have treatment as the fixed effect and the baseline average IELT as the covariate. Change from baseline in average IELTs up to weeks 2, 4, 6, 8, 10 and 12 and the interval-based change from baseline in average IELT for weeks 4, 8 and 12 will not be log-transformed prior to analyses.

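### The weeks 8–12 IELT comparison uses only men with evaluable events in that interval and can be biased in either direction if loss depends on earlier response; a supportive repeated-measures model would guard against this

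*Protocol*

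**What the plan says.** Protocol 7.3.2 introduces the secondary analyses with "The following key secondary efficacy variables will be analyzed using ANCOVA, with the treatment as factor and with baseline value as a covariate". Its list includes geometric mean and average IELT by interval, that is, "events between baseline and week 4, between week 4 and week 8, and between week 8 and week 12".

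SAP 5.3.1 carries this over: "Same ANCOVA model used in Section 5.2.1 will be used to the change from baseline in the log-transformed geometric mean IELT". It extends the same model to "change from baseline in interval-based log-transformed geometric mean IELT for weeks 4, 8" and 12, with treatment as fixed effect and baseline as covariate. There is no interval term, patient effect or within-patient covariance.

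On missing data, Protocol 7.2.1 defers to the SAP: "Data handling conventions including missing data imputation will be discussed in detail in the statistical analysis plan". The SAP's answer, in 2.3, is "Except for AE and medication onset/stop dates, missing data will not be imputed".

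The mITT population (SAP 2.1) needs a baseline IELT and some postbaseline IELT, so a man can be in mITT without a weeks 8–12 value. Only events with intravaginal ejaculation and a recorded time, or with ejaculation before penetration, are evaluable (Protocol 6.3.4.1, SAP 5.1). Providing fewer than four evaluable events a month is not a deviation (Protocol 4.6).

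**The concern.** Each interval estimate rests on whichever men have evaluable events in that interval, so the three estimates can describe different men. A man's earlier intervals predict his missing late one, but the planned model does not use them. The Wilcoxon tests in SAP 5.4 use the same observed values, and no missing-data sensitivity analysis for IELT is visible.

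Loss related to response is plausible. SAP 3.2 states: "The reason for discontinuation include adverse event, lack of efficacy, lost to follow-up, personal reasons, protocol violation and other". Withdrawal is allowed at any time (Protocol 8.8), and a couple can have an empty interval without leaving the study.

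What is at stake is the reading of late effect. The primary variable pools all 12 weeks, and the other IELT secondaries are cumulative. Only the weeks 8–12 interval separates late from early effect, and Protocol 1.5 expects a single treatment to work for several months. A difference between the early and late estimates could reflect who is left, not the drug.

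**Working it through.** **The plan's own figure.** No power, precision or dropout figure is given for the interval analyses. The nearest is Protocol Table 7–1 (two-group t-test on log IELT, one-sided 0.10). For 12 versus 12, two-fold, CV 1:
- log SD = √ln(1 + 1²) = 0.833
- SE = 0.833 × √(1/12 + 1/12) = 0.340
- noncentrality = ln 2 / 0.340 = 2.04 on 22 df, giving power 76.4% (table: 76%)

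CVs of 1.5 and 2 give 60.0% and 51.3% (table: 60% and 51%). All 27 cells reproduce within one point, so the log-normal scale below matches the plan's.

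**Inputs from the documents.**
- Pooled placebo CV 1.28 (Table 7–2): log SD = √ln(1 + 1.28²) = 0.985.
- Pooled placebo (SAP 2.3): 5 × 2 + 12 = 22. Active groups of 8 or 12.

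**Assumptions not in the documents.**
- True ratio 2.0 in every interval.
- Between-interval correlation 0.6 or 0.8; correlation with baseline 0.4.
- Exit depends on the previous interval's IELT, so data are missing at random (MAR) given observed values.
- Group sizes 12 vs 22, 12 vs 12 and 8 vs 22; 3,000 simulated trials per setting.

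**Methods compared at weeks 8–12.** (i) The planned ANCOVA on men observed in that interval. (ii) The maximum-likelihood repeated-measures estimate, with unstructured covariance and baseline-by-interval terms.

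A check with no missing data, 12 vs 22: expected SE ≈ 0.985 × √(1 − 0.4²) × √(1/12 + 1/22) = 0.985 × 0.917 × 0.359 = 0.324. The simulated SE is 0.328, identical for both methods.

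| Loss pattern | Missing by weeks 8–12, all patients | ANCOVA error in fold ratio | Repeated-measures error |
|---|---|---|---|
| None | 0 | none | none (same estimate) |
| Unrelated to response | about 19% | none | none |
| Poor responders leave both arms, same rule | 12–27% | −4% to −12% | within about 1% |
| Poor responders leave BOTOX only | 3–16% | +6% to +27% | within about 1.5% |
| Poor responders leave placebo only | 20–27% | −19% to −26% | within about 1% |

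Conversion from the log scale, for 12 vs 12 at correlation 0.8: +0.240 gives exp(0.240) = 1.27, or +27%; −0.296 gives exp(−0.296) = 0.74, or −26%. With a true ratio of 2.0, the three selective patterns read as about 1.92 to 1.76, 2.12 to 2.54 and 1.62 to 1.48. Simulation error is about 0.4/√3000 = 0.007 log units.

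The one-arm rows imply heavier loss within the affected arm:
- BOTOX only: from 0.030 × 30/8 = 11% (8 vs 22) to 0.158 × 24/12 = 32% (12 vs 12) of BOTOX men.
- Placebo only: from 0.271 × 30/22 = 37% (8 vs 22) to 0.209 × 24/12 = 42% (12 vs 12) of placebo men, so this row is a severe case.

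**Precision.** With random loss and 12 vs 22, the SE is 0.373 against 0.360 (correlation 0.6) and 0.377 against 0.346 (correlation 0.8). Over all sizes the repeated-measures SE is about 2–8% smaller. Under selective exit it ranges from about 2% larger to 5% smaller.

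**Second simulation**, with all planned arms (placebo 22, five doses of 8, one of 12) and correlations 0.6–0.9. Men with short IELT were likelier to leave.
- With 19% of placebo and 11% of BOTOX men missing, ANCOVA gave 1.88–1.93.
- With 31–32% and 17% missing, it gave 1.72–1.81.
- Repeated measures gave 1.96–2.01.

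These ANCOVA errors run from 1.93/2 − 1 = −3.5% to 1.72/2 − 1 = −14%, broadly in line with the both-arms row.

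**The case against.** A reader might infer more than the documents support:

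- *That the late estimate is biased.* No dropout rate or pattern is given, and a listed exit reason is a disposition category, not a forecast. Treatment is a single injection, so there is no continuing dosing to abandon. Cohort 6 men must complete the double-blind period to receive open-label BOTOX (Protocol 3.3.1), which gives 12 of the 22 planned placebo men a reason to stay.
- *That selective exit makes a sustained effect look like waning.* Exit of poor responders from BOTOX alone inflates the late effect. The direction is unknown.
- *That the planned analysis is materially less precise.* The gain is zero with complete data and negligible under selective exit.
- *That a repeated-measures model cures the problem.* Events without ejaculation are non-evaluable. If a strong drug effect empties an interval in this way, the loss may depend on the unseen response, and a MAR model does not correct for it.

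The error is also small against the noise. In the milder case of the second simulation (12 vs 22, correlation 0.8) the log estimate is 0.637 with SD 0.389. The bias is 0.693 − 0.637 = 0.056, or 0.14 SD. The 95% range, exp(0.637 ± 1.96 × 0.389), runs from 0.88 to 4.05. The heavier case gives 0.139/0.377 = 0.37 SD.

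The stakes are modest. The study is exploratory, SAP 1.2 names no secondary objective, and durability is an inference from Protocol 1.5. The primary and cumulative analyses keep early leavers who had any event. SAP 3.2 tabulates disposition by visit and SAP 5.1 summarises evaluable-event counts, so unequal loss would be partly visible.

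All of this limits the claim. What remains is that the planned late contrast drops men without using their earlier data, and visible loss is not the same as an analysis that allows for it.

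**Conclusion.** The concern holds in conditional form. The weeks 8–12 contrast can be biased either way if exit or absence of events is related to earlier response: by −4% to −26% or +6% to +27% of the fold ratio across the selective patterns tried, against about 1.5% at most for a repeated-measures model. These figures rest on assumed dropout, correlations and a constant two-fold effect. The largest negative values need about two-fifths of placebo men to be lost. With complete data, or loss unrelated to response, the planned analysis is unbiased. Bias, not precision, is the reason to act. The primary analysis is unaffected, so this is a worthwhile, inexpensive improvement to a secondary analysis.

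**What to change.** In SAP 5.3.1, add as a supportive analysis one mixed model for repeated measures on the three interval changes in log geometric mean IELT:

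- Terms: treatment, interval, treatment-by-interval, baseline log geometric mean, baseline-by-interval.
- Unstructured covariance common to all arms, Kenward–Roger degrees of freedom, and a prespecified simpler structure if it does not converge.
- Report each dose versus placebo in each interval. Keep the separate ANCOVAs.
- Tabulate men contributing and evaluable events per arm per interval.
- Add a sensitivity analysis for events recorded as having no ejaculation, for example taking a recorded time to withdrawal as a lower bound.

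SAP 5.3 should also settle one derivation of the interval values. It says they "will also be calculated from the above two as differences between periods", but then assigns events to intervals by study day. The model needs the latter.

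Cost: SAP wording, one extra model on variables already derived, one table and one sensitivity analysis; no new data. The small downside is a forced common covariance with only 8–12 men per active arm. With complete data the weeks 8–12 result matches the planned ANCOVA.
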